6.1.5. Safety variable

Safety data, concomitant therapies and concomitant medications are listed and summarized by contingency tables. Safety population is used for this analysis.

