Study endpoints:	Primary endpoint: 
• Change of best corrected visual acuity in ETDRS letters score at month 12 when compared with baseline (measured by the difference in ETDRS letters score between month 12 and baseline) Secondary endpoints: 
• Number of treatments with ranibizumab up to 6, 12, 18 and 24 months of treatment respectively• Mean average change in BCVA at 6, 12, 18 and 24 months after initial treatment• Macular thickness (as measured with OCT) at 6, 12, 18 and 24 months after initial treatment• Time to reach target HbA1c• Number of neovascular complications: need for panretinal laser photocoagulation (PRP)• Rates of ocular and of systemic AEs (retinal detachment, central retinal artery occlusion, endophthalmitis; rates of stroke, myocardial infarction, severe hypoglycemia)

Medical condition:	Diabetic patients with visual impairment due to diabetic macular edema (DME)								
Principal inclusion criteria:	
 • Patients with diabetic macular edema relevant to visual acuity • OCT central retinal thickness $\geq 250\mu\text{m}$ • HbA1c $> 6,5\%$ at initial visit • BCVA ≤ 0.8 and ≥ 0.05 • Age ≥ 18 years • Written patient informed consent given 								
Principal exclusion criteria:	
 • Previous treatment with intravitreal drugs in last 6 months • Vitreous hemorrhage as a consequence of proliferative retinopathy • Pregnancy • Blood pressure of $\geq 180/100$ (or uncontrolled pressures under pharmacological therapy) • Chronic systemic or ocular inflammatory/autoimmune diseases (e.g. inflammatory bowel disease, Addison's disease, Cushing Syndrome, Uveitis) • Systemic cortisone or anti-VEGF therapy • Acute systemic or ocular infectious diseases 								
Name of investigational medicinal product (IMP):	Ranibizumab (Lucentis®)								
Investigational medicinal product – dosage and method of administration:	Ranibizumab – three initial monthly intravitreal injections (0.05 mg) and subsequent injections until visual acuity reached maximum (maximum of visual acuity defined as stable visual acuity under treatment with ranibizumab on three consecutive monthly control visits)								
IMP or therapy used as a comparator – dosage and method of administration:	not applicable								
Duration of treatment:	12 months treatment period with Ranibizumab Total follow-up is 12 months (with PRN treatment option)								

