Time plan:	
 
 First patient first visit (FPFV):	01 August 2015	
 
 Last patient first visit (LPFV):	31 May 2018	
 
 Last patient last visit (LPLV):	31 May 2020	
 
 Final study report:	31 April 2021	
 
	First patient first visit (FPFV):	01 August 2015	Last patient first visit (LPFV):	31 May 2018	Last patient last visit (LPLV):	31 May 2020	Final study report:	31 April 2021
First patient first visit (FPFV):	01 August 2015								
Last patient first visit (LPFV):	31 May 2018								
Last patient last visit (LPLV):	31 May 2020								
Final study report:	31 April 2021								
Statistician:									

- Statistical methods:** For the comparison of means between two arms ANCOVA is used (normality assumption is assessed graphically and if necessary, will be tested by Shapiro-Wilk statistic. If the normality assumption is violated a nonparametric test is applied).
Repeated measurement analysis for BCVA and central retinal thickness.
Log-rank test and Cox model for time to reach target HbA1c
Chisquare test for the number of neovascular complications and AE comparisons if applicable, otherwise the Fishers exact test will be performed.
Descriptive statistics in terms of mean, standard deviation (SD), median, 25th and 75th percentiles, 95% confidence Intervals and frequency tables.
- GCP conformance:** The present trial will be conducted in accordance with the valid versions of the trial protocol, ICH Good Clinical Practice Guidelines (ICH-GCP) and applicable local regulatory requirements.
- Financing:** This investigator initiated trial is financially supported by Novartis Pharma, Nürnberg, Germany. Trial Sponsorship is taken over by Charité University Medicine Berlin.

Table of contents

Signatures	2
I. Synopsis	3
List of tables	8
List of figures	8
II. Abbreviations	9
1. Introduction	10
2. Objectives of the clinical trial	11
2.1. Rationale for the clinical trial	11
2.2. Primary objective / Hypothesis:	11
2.3. Secondary and other objectives	11
3. Rates of organisational and administrative aspects of the trial	12
3.1. Sponsor	12
3.2. Principal Coordinating Investigator	12
3.3. Statistics	12
3.4. Data Monitoring Committee	12
3.5. Further committees	12
3.5.1. Steering Committee	12
3.5.2. Advisory Committee	12
3.5.3. Imaging Review Board	12
3.6. Study laboratories and other technical services	13
3.7. Central organisation units	13

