4.7.1.2. Secondary target variables

- Number of treatments with Ranibizumab up to 6, 12, 18 and 24 months of treatment respectively
- Mean average change in BCVA at 6, 12, 18 and 24 months after initial treatment
- Macular thickness (as measured with OCT) at 6, 12, 18, and 24 months after initial treatment
- Time to reach target HbA1c
- Number of neovascular complications: need for panretinal laser photocoagulation (PRP)
- Rates of ocular and of systemic AEs (retinal detachment, Central retinal artery occlusion, endophthalmitis; and rates of stroke, myocardial infarction, severe hypoglycemia)

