6.1.1. Trial populations

The first dataset for analysis is derived from the intention-to-treat (ITT) population. This dataset includes all trial subjects enrolled into the trial, randomised to treatment groups and received at least one injection of ranibizumab- no exclusions.

The second dataset for analysis is derived from the per-protocol (PP) population. This dataset includes all trial subjects who were treated according to protocol (i.e. they received at least 3 injections of ranibizumab and do not meet any exclusion criteria) and reached/provided at least one endpoint of main interest (i.e. after 6 months of follow-up).

The third dataset for analysis is the safety population. This population includes all trial subjects who received any ranibizumab treatment.

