6.1.4. Secondary efficacy variables

Different statistical methods will be applied for analysis of secondary endpoints.

For the number of treatments at 6, 12, 18 and 24 months, an ANOVA without any covariates will be applied at each endpoint 6, 12, 18 and 24 months.

The data of change in BCVA and macular thickness at 6, 12, 18 and 24 months are analysed by repeated measures analysis of variance (assuming missing at random, MAR). The missing values for BCVA and macular thickness are imputed by the last observation carried forward (LOCF). The treatment by time interaction will be included in both statistical models but the baseline value will only be included in the change in BCVA analysis since the macular thickness will not be adjusted by the baseline value in this analysis.

The change in BCVA and macular thickness with respect to baseline values is calculated at 6, 12, 18 and 24 months. For each time point, the change values are described statistically by mean, standard deviation, and 95% confidence interval.

Time to reach target HbA1c is evaluated by log-rank test and hazard ratio in terms of a Cox proportional hazard model. The results are visualised by Kaplan-Meier curves. No covariates are included in the model.

The number of neovascular complications in two treatment arms is compared by frequencies and a chi-square test if applicable (the chi-squared test will not be used when the absolute frequency in any of the cells of the contingency table is below 5), otherwise the Fishers exact test will be performed.

ITT population is used for all secondary efficacy analyses.

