7.2.3. Causal relationship between adverse event and investigational medicinal product

The investigator will assess for every AE whether a causal relationship with the IMP can be assumed or not. The assessment includes consideration of the nature and type of reaction, the temporal relationship with the IMP, the clinical status of the trial subject, concomitant medication and other relevant clinical factors. If the event is considered due to lack of efficacy or as a symptom or sign of the underlying disorder, no causal relationship will be assumed.

The following definitions are used to assess the causal relationship between all AEs and the IMP (WHO Causality Assessment of Suspected Adverse Reactions):

- Certain: A clinical event, including laboratory test abnormality, occurring in a plausible time relationship to drug administration, and which cannot be explained by concurrent disease or other drugs or chemicals. The response to withdrawal of the drug (dechallenge) should be clinically plausible. The event must be definitive pharmacologically or phenomenologically, using a satisfactory rechallenge procedure if necessary.
- Probable/likely: A clinical event, including laboratory test abnormality, with a reasonable time sequence to administration of the drug, unlikely to be attributed to concurrent disease or other drugs or chemicals, and which follows a clinically reasonable response on withdrawal (dechallenge). Rechallenge information is not required to fulfill this definition.
- Possible: A clinical event, including laboratory test abnormality, with a reasonable time sequence to administration of the drug, but which could also be explained by concurrent disease or other drugs or chemicals. Information on drug withdrawal may be lacking or unclear.
- Unlikely: A clinical event, including laboratory test abnormality, with a temporal relationship to drug administration which makes a causal relationship improbable, and in which other drugs, chemicals or underlying disease provide plausible explanations.
- Conditional/unclassified: A clinical event, including laboratory test abnormality, reported as an adverse reaction, about which more data is essential for a proper assessment or the additional data are under examination.
- Unassessable/unclassifiable: A report suggesting an adverse reaction which cannot be judged because information is insufficient or contradictory, and which cannot be supplemented or verified.

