7.3.4. Review and reporting of changes in the risk-benefit ratio

Without delay, and at the latest within 15 days of the decision for the need to do so, the sponsor or PCI will inform the competent supreme federal authority, the ethics committee responsible of any events or factors that mean that the risk-benefit ratio of the IMP has to be reviewed. These consist of especially:

- Individual reports of expected serious ADRs with an unexpected outcome
- A clinically relevant increase in the rate of occurrence of expected SADR
- SUSARs in trial subjects who have already completed the follow-up period of the clinical trial ("end-of-trial visit")
- Factors emerging in connection with trial conduct or the development of the IMP that may affect the safety of persons concerned.

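### Severe hypoglycaemia is named as a rate, but the planned tables and tests, validly applied, leave out repeat episodes and follow-up time

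*Combined protocol and SAP*

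**What the plan says.** - **Endpoint.** Section 4.7.1.2 lists "Rates of ocular and of systemic AEs" as a secondary target variable and names severe hypoglycaemia among the systemic events; the synopsis does the same. Neither place defines the rate, its denominator or severe hypoglycaemia.
- **Analysis, section 6.1.5.** "Safety data, concomitant therapies and concomitant medications are listed and summarized by contingency tables". The safety population is used, of which section 6.1.1 says: "This population includes all trial subjects who received any ranibizumab treatment". No counting unit, exposure time, method for recurrent events or split by arm is given.
- **Analysis, synopsis.** "Chisquare test for the number of neovascular complications and AE comparisons if applicable, otherwise the Fishers exact test will be performed". Section 6.1.4 carries this rule over for neovascular complications only: "The number of neovascular complications in two treatment arms is compared by frequencies and a chi-square test if applicable". Section 6.1.5 names no test.
- **Data.** Section 7.2.1 records every adverse event in the reporting period with onset and resolution. Section 7.1.3 has a recurrent serious event reported as follow-up to the first one. Section 7.1.1 and footnote 2 of Table 3 end adverse-event documentation 30 days after ranibizumab stops. Serious events are reported until 4 weeks after participation ends (section 7.1.3).
- **Oversight.** There is no data monitoring committee (section 3.4) and no interim analysis (section 6.1.7). The annual safety report (section 7.4) specifies no display by arm. Causality is rated against the drug that both arms receive: "The investigator will assess for every AE whether a causal relationship with the IMP can be assumed or not".

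**The concern.** Both arms receive ranibizumab; what is randomised is the intensity of glycaemic control (section 4.2). Severe hypoglycaemia is therefore the main harm to set against any gain in letters. It can recur in the same patient, and the withdrawal rules in sections 4.4 and 4.6.8.1 may make follow-up unequal.

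A chi-square or Fisher test needs independent units, so a valid version classifies each patient as having had an episode or not. One episode then counts the same as six, and a patient seen for 5 months the same as one seen for 24. The endpoint is called a rate, yet no planned analysis produces one with person-time below the line.

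Two data rules would weaken a rate computed afterwards. Filing recurrences under the first serious event puts the episode count at risk. Collection of non-serious events ends with the injections, while the diabetes programme runs to month 24. Section 2.1 expects the programme to reduce re-treatment, so the collection window could close earlier in the intensified arm.

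**Working it through.** **1. Arm size (the plan's own figure).** From section 6.2: difference 2.0, SD 3.5, two-sided 5%, power 85%. Normal approximation: n = 2 × (1.960 + 1.036)² × (3.5/2.0)² = 2 × 8.98 × 3.0625 ≈ 55 per arm. The t-test gives 55.97, so 56. With the drop-out allowance, 56 × 1.07 = 59.92, so 60. The figure reproduces. It fixes the arm size and says nothing about hypoglycaemia.

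**2. What a patient count can detect.** With 60 per arm, Fisher's two-sided test first falls below 0.05 at 0 v 6 patients (p = 0.027), 1 v 8 (p = 0.032) and 2 v 10 (p = 0.029).

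**3. What a patient count leaves out.** Assumed: episode counts are gamma-Poisson with mean μ = rate × 2 years and dispersion k. Then P(at least one) = 1 − (1 + kμ)^(−1/k). For 0.1 v 0.3 per patient-year, μ = 0.2 and 0.6, and expected episodes are 60 × 0.2 = 12 and 60 × 0.6 = 36, in total 48.

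| k | Patients with an episode | Share of episodes not counted | Risk ratio shown (true rate ratio 3) |
|---|---|---|---|
| 1 | 60(1 − 1/1.2) = 10.0; 60(1 − 1/1.6) = 22.5 | 1 − 32.5/48 = 32% | 2.25 |
| 2 | 60(1 − 1.4^−0.5) = 9.3; 60(1 − 2.2^−0.5) = 19.6 | 1 − 28.8/48 = 40% | 2.10 |
| 4 | 60(1 − 1.8^−0.25) = 8.2; 60(1 − 3.4^−0.25) = 15.8 | 1 − 24.0/48 = 50% | 1.93 |

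Over a wider grid (control rate 0.05 to 0.4, rate ratio 2 or 3, k from 0.5 to 2), the share not counted runs from 11% to 70%, and a true rate ratio of 3 shows as a risk ratio of 1.54 to 2.60.

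**4. Power (simulation under the same model, full 24 months for everyone).**

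| Rates per patient-year | k | Fisher on patients | Permutation test on episodes |
|---|---|---|---|
| 0.1 v 0.3 | 1 | 68% | 82% |
| 0.1 v 0.3 | 2 | 49% | 68% |
| 0.1 v 0.3 | 4 | 33% | 55% |
| 0.05 v 0.1 | 1 to 4 | about 8–18% | about 13–20% |

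With no difference between arms, both tests rejected in 2.4–4.6% of runs. A negative binomial Wald test with dispersion taken as known, which is slightly optimistic, gave 84% against 67% for Fisher at 0.1 v 0.3 with k = 1, and 23% against 16% at 0.05 v 0.1 with k = 1.

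The simulation has no withdrawals, so it measures the loss from ignoring repeats, not the loss from ignoring follow-up time.

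**The case against.** The strongest reply is that the plan does less harm than a quick reading suggests. Four stronger readings are tempting, and the documents do not support them.

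- *Repeat episodes are lost.* They are not. Section 7.2.1 dates each event and section 6.1.5 lists them, so a rate could be derived. They are left out of the planned comparison, and the follow-up rule in section 7.1.3 puts the count of serious repeats at risk.
- *Arms are never compared.* The synopsis tests for adverse-event comparisons imply a final comparison in a two-arm trial. What is missing is a scheduled comparison during the trial.
- *Risk-benefit review is confined to ranibizumab.* Section 7.3.4 opens with "any events or factors that mean that the risk-benefit ratio of the IMP has to be reviewed", but its last trigger also covers trial conduct. The termination rule in section 4.5.2 concerns the balance for the trial subject.
- *An excess in the intensified arm would trigger no review.* Serious events reach the sponsor within 24 hours whatever the cause (section 7.3.1), the sponsor or coordinating investigator assesses each one (section 7.3.2), treatment is not blinded (section 4.6.7), and the annual report covers the safety of trial subjects (section 7.4).

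It is also fair that patient counting is inferred, since section 6.1.5 states no unit; that section 6.1 leaves details to a later analysis plan; that this is an exploratory trial sized for visual acuity; that section 4.4 asks for follow-up after treatment stops; and that patients with at least one event is a legitimate summary. If severe hypoglycaemia is always handled as a serious event, the 30-day limit matters less, because serious-event reporting runs past the end of participation. With no definition given, this cannot be settled.

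These points narrow the concern. None of them supplies a denominator, a method for recurrent events or a scheduled look by arm.

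**Conclusion.** The concern holds in a limited form. The plan names a rate, provides methods that validly count patients, and has collection rules that do not guarantee a complete episode count over the period of the diabetes programme. The synopsis and section 6.1.5 also differ on whether adverse events are tested at all.

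The size is conditional. All event rates and dispersions above are assumptions. If severe episodes are fairly common and cluster in some patients (0.1 v 0.3 per patient-year), power rises by about 14 to 22 points and 32–50% of episodes would otherwise not be counted. If they are rare (0.05 v 0.1, or 0.02 v 0.06), the gain is only about 2 to 5 points and neither method would detect much. Even then, a rate ratio with its interval describes the endpoint as named. The primary analysis is unaffected.

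**What to change.** 1. **Section 6.1.5.** State the definition of severe hypoglycaemia to be used. Report it by randomised arm as (a) patients with at least one episode and (b) episodes per patient-year, with a rate ratio and 95% CI, for example from a negative binomial model with the log of time under adverse-event collection as offset. If an arm has no episodes, give counts and person-time.
2. **Synopsis.** Bring the statistical methods into line with section 6.1.5, and say which adverse events, if any, are tested.
3. **Sections 7.1.3 and 7.2.1.** Enter each episode in the database with its own date, even where the serious-event form is filed as follow-up to an earlier one.
4. **Section 7.1.1 and Table 3.** Collect this event for the whole of study participation, so that the count and the offset cover the same period.
5. **Section 7.4.** Add a table of severe hypoglycaemia by arm to each annual safety report.

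The cost is analysis-plan and protocol wording, slightly more data collection after injections stop, and one table a year.

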6.1.6. Sensitivity and Subgroup analyses

A sensitivity analysis for the primary endpoint based on the PP population will be performed.

Another sensitivity analysis will assess the influence of the assumption of normality for the primary analysis by transforming the data with the natural logarithm. The ANCOVA described in section 6.1.3 will be applied in the same way on the transformed data.

The primary and secondary endpoint except number of neovascular complications and rates of ocular and of systemic AEs will be analysed by descriptive statistics and statistical methods mentioned above within the following subgroups defined by the following potentially prognostic baseline variables:

- HbA1c: $\geq 9\%$
- HbA1c: $\geq 7,5\%$, $< 9\%$

- HbA1c: $\geq 6,5\%$, $< 7,5\%$
- Intravitreal treatment with ranibizumab before trial entry (yes vs no)
- Size of macula edema $>400\mu\text{m}$
- BCVA (>65 vs ≤ 65)

For the sake of subgroup analysis, the ITT population will be used.

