4.4. Withdrawal of trial subjects after trial start

Study subjects will be early discontinued from participation in the study if

- they withdraw consent from participating in the study
- no response to the ranibizumab treatment is observed, defined as persisting macular edema without any reduction of central retinal thickness after 3 consecutive monthly injections
- they present visual loss defined as ≥ 30 ETDRS Letters when compared with the baseline
- they develop vitreous bleeding due to active neovascularisation of the retina or optic disc confirmed by fluorescein angiography with need of surgical treatment (vitrectomy)
- any other clinical adverse event (AE), laboratory abnormality, illness or other medical condition or situation occurs that would not go along with the best interest of the patient in case of continuing the participation.

Note: Each patient should be followed-up even if the study treatment is discontinued.

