4.6.1. Treatments to be given

In all patients (in both study arms) the diabetic macular edema will be treated with intravitreally given ranibizumab.

Dosage and administration of Ranibizumab

Injections are administered according to the current summary of product characteristics Lucentis®, i.e. monthly until maximum BCVA can be observed:

Starting at visit 1, ranibizumab will be administered intravitreally in a multiple-dose regimen of 0.5 mg of ranibizumab every month for a total of 3 injections and as a PRN treatment thereafter (subsequent injections until maximum BCVA is observed).

Injection is discontinued when

- no BCVA improvement in spite of treatment is seen after the first three injections (i.e. after three consecutive monthly visits)

BCVA assessments will take place monthly. Monthly injections are resumed when

- decrease in BCVA due to worsening of DME in the opinion of the investigator is observed

Injections are continued until BCVA improvement is seen after three consecutive monthly visits.

If a subject is unable to receive study drug because of medical or personal reasons, treatment should be resumed within 2 weeks of the scheduled treatment. If a subject is unable to receive study drug within 2 weeks of the scheduled treatment, the subject will be allowed to miss the scheduled dose and resume treatment at the next regularly scheduled time. Dosing should not occur more frequently than every 4 weeks. Missed doses will not be replaced.

Ranibizumab Injection

Procedures will be implemented to minimise the risk of potential adverse events associated with serial intraocular injections (e.g., endophthalmitis). Aseptic technique must be observed by clinic staff involved in the injection tray assembly, anesthetic preparation and administration, and study drug preparation and administration. In addition to the procedures outlined in the protocol, added safety measures in adherence to specific institutional policies associated with intraocular injections should be observed.

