6.1. Statistical and analytical plan

This is a two-arm, monocentre, therapeutic-exploratory clinical trial with 120 patients randomly assigned to treatment arms. Though the primary analysis is done at 5% significance level (two-sided). The essentials of the statistical analysis are outlined below. Further details will be laid down in the statistical analysis plan.

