6.1.3. Primary target variable

The primary endpoint will be the change of best corrected visual acuity in ETDRS Letters score at month 12 when compared with baseline. This endpoint will be analysed by analysis of covariance (ANCOVA) with the baseline value as covariate (type II SS will be used since no interaction terms are included in the model).

The null hypothesis is:

$$H_0: \mu_{iDC} = \mu_{rDC}$$

and the alternative hypothesis is:

$$H_1: \mu_{iDC} \neq \mu_{rDC}$$

where μ_{iDC} is the mean of the differences in ETDRS Letters score between month 12 and baseline for the investigational arm (intensified diabetic control) and μ_{rDC} is the mean of the differences in ETDRS Letters score between month 12 and baseline for the control arm (regular diabetic control).

ITT population is used for the primary efficacy analysis. If no ETDRS Letter score is available at month 12 the closest measurement (could be before or after 12 month) which was at least after 3 months will be used for the analysis.

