6.1.8. Handling of missing data

If not stated otherwise no imputations of missing values will be performed.

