6.2. Sample size calculation

The calculation of the sample size is based on the primary endpoint. It is of interest to discover the difference between two treatment groups, and we assume that the average difference between treatments in the primary endpoint is 2.0 ($\delta=2.0$). Assuming the standard deviation of the change of best corrected visual acuity in ETDRS letters score over 12 months be $\sigma=3.5$. Then, the study is designed to detect a decrease of 0.571 times of standard deviation in the primary endpoint for the treatment arm with intensified diabetic control program ($\delta/\sigma\approx 0.571$). With a two-sided alpha of 5% and a power of 85%, a sample size of 112 patients is required to detect this difference. Given the allocation ratio of 1:1 between two treatment arms, 56 patients per arm are required. In order to take drop-outs into account, approx 7% increase in sample size is anticipated which leads to the randomisation of 60 patients per treatment arm ($56*1.07=60$). Thus, altogether, 120 patients will be included in the trial. Sample size calculation was performed with SAS 9.4.

7. Safety

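### The normality sensitivity analysis takes the logarithm of a change score that can be zero or negative, and the synopsis lets an unnamed nonparametric test replace the primary ANCOVA

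*Combined protocol and SAP*

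**What the plan says.** Section 6.1.3 defines the primary endpoint as the month-12 minus baseline change in ETDRS letters, with hypotheses on the mean change per arm. On the analysis it says: "This endpoint will be analysed by analysis of covariance (ANCOVA) with the baseline value as covariate". No normality condition or alternative test is attached.

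Section 6.1.6 adds a sensitivity analysis for normality, done by "transforming the data with the natural logarithm. The ANCOVA described in section 6.1.3 will be applied in the same way on the transformed data". It gives no offset and no rule for values at or below zero. On missing values, section 6.1.8 says: "If not stated otherwise no imputations of missing values will be performed".

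The synopsis (Statistical methods) also names ANCOVA, but has normality judged from graphs, with Shapiro-Wilk where that seems needed. It then adds: "If the normality assumption is violated a nonparametric test is applied". The test is not named and no threshold is set. Section 6 does not repeat this rule.

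The protocol foresees patients who do not gain vision. Section 4.6.1 provides for the case that "no BCVA improvement in spite of treatment is seen after the first three injections". Section 4.4 lists as a ground for discontinuation that "they present visual loss defined as" 30 letters or more from baseline.

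**The concern.** **The log analysis.** The logarithm does not exist for a change of zero or less, so the analysis cannot be run on all patients as written. Someone must later decide whether to drop those patients, shift the scale or log something else. Dropping them selects on the outcome and removes more patients from the arm that did worse. The analysis then mixes the normality question with selective deletion and a change of scale, so its disagreement with the primary result would say little about normality.

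**The switch.** Section 6.1 calls the trial exploratory but sets a two-sided 5% primary test. The synopsis line leaves three things open until the outcomes have been seen: which test is used, whether baseline is adjusted for, and whether the hypothesis still concerns a mean difference. Section 6.1.3 leaves none of them open.

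**Working it through.** **Inputs.** Section 6.2 gives a difference of 2.0 letters, an SD of 3.5, 56 patients per arm and 60 randomised per arm. The mean gain in the control arm is not in the documents; it is assumed here at 2, 4, 6, 8 and 10 letters.

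**1. The plan's own figure.** Section 6.2 states: "With a two-sided alpha of 5% and a power of 85%, a sample size of 112 patients is required to detect this difference". The two-sample t-test has noncentrality (2.0/3.5) × √(56/2) = 3.02 with 110 degrees of freedom, which gives power 0.850 at 56 per arm, 112 in total. The figure is reproduced, and neither point below changes it.

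**2. Share of patients with no logarithm.** For normal changes with mean μ, P(change ≤ 0) = Φ(−μ/3.5). Letter scores are whole numbers, so a change of exactly 0 also counts, and the share becomes Φ((0.5 − μ)/3.5). The intensified arm has μ two letters higher.

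**3. Difference among those left.** The mean of the positive changes is μ + SD·φ(μ/SD)/Φ(μ/SD). At a control gain of 4 this is 4.83 in the control arm and 6.34 in the intensified arm, a difference of 1.50 instead of 2.0.

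| Assumed control gain | Undefined, control vs intensified (continuous) | Of 120 | Difference left | Undefined (whole letters) |
|---|---|---|---|---|
| 2 | 28% vs 13% | 25 | 1.18 | 33% vs 16% |
| 4 | 13% vs 4% | 10 | 1.50 | 16% vs 6% |
| 6 | 4% vs 1% | 3 | 1.77 | 6% vs 2% |
| 8 | 1% vs 0.2% | 0.8 | 1.92 | 2% vs 0.3% |
| 10 | 0.2% vs <0.1% | 0.1 | 1.98 | 0.3% vs <0.1% |

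On the whole-letter scale, about 30 of 120 patients are lost at a gain of 2 and 13 at a gain of 4, with differences left of 1.09 and 1.42. At an assumed SD of 7 and a gain of 4, the continuous shares are 28% vs 20% and the difference left is 1.09.

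**4. Effect on the test.** There were 4,000 simulated trials per setting with 56 per arm, normal changes rounded to whole letters and baseline assumed N(60, 12). The primary ANCOVA was compared with the same model on ln(change), using only patients with change > 0.

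| Assumed control gain | ANCOVA power | Log-ANCOVA power | Opposite 5% verdicts |
|---|---|---|---|
| 2 | 84-85% | 42% | 45% |
| 4 | 84-85% | 60% | 27% |
| 6 | 84-85% | 72% | 17% |
| 8 | 84-85% | 78% | 11% |
| 10 | 84-85% | 80% | 7% |

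At a gain of 10 almost nobody is lost, so the remaining disagreement comes from the change of scale.

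**5. The switch.** The synopsis line cannot be read as covering only secondary endpoints, because the only ANCOVA named as such in section 6 is the primary one. As an illustration, suppose the unnamed test were Mann-Whitney on the change (gain 4, SD 3.5, 4,000 trials per setting):

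| Assumed baseline-change correlation | Mann-Whitney power | ANCOVA power | Opposite verdicts |
|---|---|---|---|
| 0 | 83% | 84% | 5% |
| −0.3 | 82% | 87% | 8% |
| −0.5 | 82% | 93% | 13% |

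**The case against.** The strongest reply is that the heavy losses come from one choice, silent deletion, which section 6.1.6 does not order. It says only that the data are logged. In simulation under the same assumptions, logging the raw letter scores (with log baseline as covariate) kept power at 83-84%, and shifting the change so that its minimum is 1 gave 79-81%. This stands as a limit on the size: the lowest powers above belong to deletion. It does not rescue the text. Neither repair is written, each would need its own sentence, and logging raw scores tests a ratio rather than the difference in H0.

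The supporting sections can also be pressed too far. Section 6.1.8 concerns missing values and does not forbid an offset. The case quoted from section 4.6.1 concerns the first three injections, not month 12. Both remarks are fair. The change is still signed by definition, and section 4.4 foresees large losses.

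On the switch, a strictly applied rule would do little to the error rate. With a t-test standing in for ANCOVA, Mann-Whitney for the unnamed test and a fixed Shapiro-Wilk trigger, simulated type I error was 4.8%, 5.7% and 4.8% for normal, t(3) and exponential data. A rank-based ANCOVA would also keep the baseline. The objection therefore removes any claim of inflation but leaves the discretion and the conflict. Section 6.1 defers further details to an SAP, but nothing in the documents settles either point.

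A permutation test, finally, nearly repeats the ANCOVA: in simulation the verdicts differed in only 0.3-1.0% of trials. Free permutation also ignores the randomisation blocks. The planned ANCOVA ignores them too, and close agreement is what should be seen if the primary test does not lean on normality.

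**Conclusion.** Both points hold and should be fixed. The log analysis fails as written for every patient without a gain. How many that is rests on an assumed control-arm gain: from about 25 of 120 at 2 letters to about 0.1 at 10 (SD 3.5, difference 2.0, continuous scale; more with whole letters). The power loss and the opposite verdicts assume in addition that undefined values are dropped. This point is confined to a sensitivity analysis.

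The synopsis switch concerns the primary test itself and is a direct conflict with section 6.1.3. The harm is discretion over the test, the baseline adjustment and the hypothesis after outcomes are known. Its numerical size depends on an assumed test and assumed correlations. The sample size is unaffected by either point.

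**What to change.** In the synopsis, delete the nonparametric switch for the primary endpoint and write:

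> The primary endpoint is analysed by ANCOVA of the change with the baseline value as covariate, whatever the normality assessment shows.

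In section 6.1.6, replace the log-transformation sentences by:

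> The influence of the normality assumption is assessed by a two-sided permutation test (10,000 permutations of the arm label) of the baseline-adjusted mean difference in change in ETDRS letters at month 12, ITT population, reported beside the primary ANCOVA.

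This test is defined for every signed change and keeps the mean difference in H0. In simulation (2,000 trials per setting, 499 permutations each, 56 per arm, SD 3.5, gain 4), its type I error was 4.2%, 5.5% and 5.1%, and its power for a 2.0-letter difference 85%, 85% and 87%, under normal, exponential-skewed and t(3) changes.

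The cost is a change of wording in two places, with no extra data or patients.
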